**b) NIH Stroke Scale (NIHSS) Total Score:**

The NIHSS Total Score evaluations will be summarized at baseline (pre-procedure) and follow-up (6 and 12 months post-procedure); change from baseline at 6 and 12 months will also be summarized. The percentage of subjects who show a worsening from baseline (increase of 4 points or more) will also be presented.

Observed scores and change from baseline will also be presented for NIHSS excluding scores on the aphasia subscale.

**c) Adverse Events and Clinical Complications:**

Adverse Events (AEs), including complications associated with an untoward medical occurrence, from the start of the index procedure until completion of the 12 month follow-up will be coded using the MedDRA system and summarized with frequencies. Serious adverse events (SAEs), device- or procedure-related AEs, unanticipated adverse device effects (UADEs) and deaths will be presented.

AEs will be presented for the following study periods: 1) peri-procedure – i.e., from the start of the procedure until 24 hours post-procedure; and, 2) through 12 month follow-up – i.e., from 24 hours post-procedure through the 12 month visit or premature termination.

**d) Reduced TICI Flow:**

The percentage of target aneurysms in which a new occurrence of unintentional and persistent reduced TICI flow (TICI score of 0 or 1) is observed at the target vessel during the index procedure as a result of a mechanical obstruction such as dissection or luminal thrombus will be evaluated.

**e) Bleeding Complications:**

The number and percentage of subjects who experience a procedure-related hemorrhagic event which requires any of the following will be evaluated: blood transfusion, surgical intervention, a new hospitalization, or lengthening of hospital stay. The complications of hematoma requiring treatment (i.e., a hematoma > 5 cm in diameter occurring at the access site) and retroperitoneal bleeding will be reported as hemorrhagic events.

**f) In-stent Stenosis (Acute, and 6 Months):**

The percentage of aneurysms in which in-stent stenosis is documented immediately post-procedure (acute), and up to and including 6 months post-procedure, will be evaluated.

Acute in-stent stenosis will be further characterized by whether it results from vasospasm, and whether or not the vasospasm was responsive to medication.

**g) Thrombosis:**

The percentage of aneurysms in which thrombosis is documented up to and including 6 and 12 months post-procedure will be evaluated. Thrombosis is defined as in-stent thrombosis.

**Ancillary Endpoint**

**Stent Movement/Migration:**

Incidence of stent movement and/or migration from the start of the index procedure until completion of the 12 month follow-up

**Safety Follow-up through 24 months post-procedure**

Subjects will be followed through 24 months post-procedure, and their outcomes will be summarized in a supplemental safety follow-up report:

- All adverse events
- Rupture of the index aneurysm beyond 24 hours post-treatment
- Major ipsilateral stroke more than 1 month post-treatment
- Ipsilateral parenchymal hemorrhage more than 1 month post-treatment

**Sample Size Determination:**

Both primary effectiveness and primary safety endpoint analyses will be conducted on the MITT population, where subjects with missing data at the time of endpoint analysis will be imputed as last observation carried forward (LOCF). Hence all subjects in the MITT population with post-procedure data are deemed to be evaluable for the purpose of MITT analyses. Subjects who receive the device but in whom there is no post-procedure data will be treated as failures for the primary effectiveness analysis; subjects who do not receive the device because of treatment failure due to reasons associated with the device will also be treated as failures. Subjects with no post-procedure endpoint data upon which to base a LOCF imputation will be excluded from the primary safety endpoint analyses; it is anticipated that fewer than 7% of MITT subjects will be excluded from either primary effectiveness or primary safety endpoint analyses. Subjects who are enrolled but who are found to be ineligible for treatment with ENTERPRISE at the time of the pre-procedure angiogram will be replaced. Subjects in whom treatment with ENTERPRISE is attempted but who discontinue study participation prematurely will not be replaced.

The study design is a group sequential design, wherein after N=160 subjects have been enrolled, treated, and followed for a minimum of 6 months post-procedure, an interim analysis will be conducted to determine whether or not to terminate the study early for futility or tentative success.

The study will terminate early for tentative success if the unadjusted 2-sided normal approximation p-value for testing the primary effectiveness endpoint (RCAO vs. the PG of 35%) is less than 0.031, and will terminate early for futility if this p-value is greater than 0.358. If the stopping rule is met for the trial to stop early for tentative success, a final confirmatory analysis will be conducted when all subjects have reached 12 months post-procedure; a p-value threshold of 0.031 will be used for this final confirmatory analysis. If neither of these interim analysis criteria for stopping the trial early is met, or if the confirmatory analysis for early success is not satisfied, then enrollment will commence until a total sample of N=320 subjects have been enrolled (including the original N=160), and all subjects will be followed for a minimum of 12 months post-procedure at which time the final primary endpoint analysis will be conducted. In this final primary endpoint analysis, the study will be deemed to be successful if the unadjusted 2-sided normal approximation p-value for testing the primary effectiveness endpoint (RCAO vs. the PG of 35%) is less than 0.031.

The statistical power to stop early for success at the interim analysis is approximately 79% if the true RCAO is 47% in the general population and there are at least 150 evaluable MITT subjects (with post-procedure data) for this interim analysis. The statistical power at the final endpoint (if the study continues to full enrollment) is 87.7% if the rate of complete occlusion in the general population is 44% and there are 300 evaluable MITT subjects (with post-procedure data) for this final analysis. With the group-sequential design of this study and the specified interim and final analyses for the primary endpoint, including the sample sizes at which analyses will be conducted and the p-value thresholds for determining study success in the respective analyses, the overall probability of a Type 1 error in this study ( $\alpha$ , 2-sided) is maintained below 0.05.

There are two primary safety endpoints with formal hypotheses that will be tested, and the following are estimates of statistical power for each of these respective endpoints at the time of the interim analysis. For each respective endpoint, the purpose of the hypothesis test is to ensure that the 2-sided 95% upper confidence limit for the estimate is less than a stated performance goal for the

endpoint. The performance goal, expected outcome, and estimated statistical power based upon a sample size of N=150 evaluable subjects (with post-procedure data) are provided for each respective endpoint.

a) Major ipsilateral stroke/death at 12 months:

- Performance goal = 25%. The upper confidence limit of a 2-sided 95% confidence interval for the proportion of subjects who experience major ipsilateral stroke and/or death through 12 months post-procedure will be observed to be less than 25%.
- Expected rate of major ipsilateral stroke and/or death is not greater than 14%.
- Statistical power  $\geq 92.5\%$ .

b) In-stent Stenosis at 12 months

- Objective performance criterion = 15%. The upper confidence limit of a 2-sided 95% confidence interval for the rate of in-stent stenosis will be observed to be less than 15%.
- Anticipated rate of in-stent stenosis is not greater than 6%.
- Statistical power = 95.5%.

**Enrollment Start Date,  
Enrollment Phase and  
Follow-up Schedule:**

The study is expected to start Q3 2015. The initial enrollment phase is expected to take 48 months. A 6-month pause in enrollment will occur after 160 subjects have been enrolled for an interim analysis to be conducted to determine if the study should stop early for futility or tentative success. If the trial is not terminated early, then enrollment will continue up to a full enrollment of 320 subjects, which is anticipated to take an additional 12 months.

Subjects will be followed through 24 months with assessments at discharge, 30 days, 6 months, 12 months, 18 months and 24 months with a follow-up angiography (digital subtraction angiography) being performed at 6, 12 and 24 months for all subjects.

If a subject experiences indications that in-stent stenosis or delayed hydrocephalus is occurring, additional follow-up

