## 9.7 Hypotheses

### **Primary Efficacy Endpoint: Rate of Complete Occlusion (RCAO) according to the Raymond Scale**

The primary efficacy endpoint analysis will be to demonstrate that the RCAO is significantly greater than a performance goal (PG) of 35%. The null and alternative hypotheses for this endpoint are as follows:

Null hypothesis  $H_0$ : RCAO  $\leq$  35%

Alternative hypothesis  $H_A$ : RCAO  $>$  35%

**Decision Criterion:** The decision will be made to reject the null hypotheses  $H_0$  and conclude the alternative hypothesis  $H_A$  either of the following occur:

1. At the interim analysis (when the first N=160 enrolled subjects have reached a minimum of 6 months post-operatively), the unadjusted 2-sided normal approximation p-value for testing the primary effectiveness endpoint (RCAO vs. the PG of 35%) is less than 0.031. The conclusion of this analysis will be a tentative conclusion; if this stopping rule for tentative success is met, a final confirmatory analysis will be conducted when all subjects have reached 12 months post-procedure, and a p-value threshold of 0.031 will be used for this final confirmatory analysis.
2. At the final analysis when all N=320 subjects have been followed for a minimum of 12 months post-procedure, the unadjusted 2-sided normal approximation p-value for testing the primary effectiveness endpoint (RCAO vs. the PG of 35%) is less than 0.031.

This primary efficacy endpoint analysis will be conducted on the MITT population.

**Note:** The study will be deemed to be a success if this primary efficacy endpoint null hypothesis (on the MITT population with data from all sites combined) is rejected in favor of the alternative hypothesis.

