#### **4: Dataset Flow Diagram for Enrolled Subjects**

True RAO in the Patient Population	Overall Power to demonstrate Primary Efficacy (at Interim or Full Enrollment)	Probability of Stopping Early for Success (Interim Analysis)	Probability of Study Success at Full Enrollment if Not Stopped at Interim Analysis	Probability of Stopping Early for Futility (Interim Analysis)
0.35	2.70%	1.40%	2.90%	60.80%
0.37	10.60%	4.60%	12.40%	54.80%
0.4	41.40%	18.00%	40.90%	32.20%
0.42	68.10%	33.90%	62.60%	17.60%
0.43	79.10%	43.30%	72.10%	12.10%
0.44	87.70%	53.20%	80.50%	8.00%
0.45	93.30%	62.70%	86.90%	4.90%
0.46	96.80%	71.70%	91.80%	2.90%
0.47	98.60%	79.30%	95.00%	1.60%
0.5	99.90%	93.90%	99.30%	0.20%

An estimate of the overall Type 1 error rate for this study design can be seen in the first row of this table, where the true RAO in the patient population is equal to the performance goal of 35% for the Primary Efficacy Endpoint; this estimated Type 1 error rate is 2.7% (2-sided), which is below 5%. An estimate of overall statistical power is 87.7% if the true RAO is 44% in the patient population, and the likelihood of stopping early for tentative study success is approximately 79.3% if the RAO in the patient population is 47%. The likelihood of stopping early for futility is approximately 54.8% if the RAO in the patient population is 37%.

There are two primary and secondary safety endpoints with formal hypotheses that will be tested, and the following are estimates of statistical power for each of these respective endpoints at the time of the interim analysis. For each respective endpoint, the purpose of the hypothesis test is to ensure that the 2-sided 95% upper confidence limit for the estimate is less than a stated performance goal for the endpoint. The performance goal, expected outcome, and estimated statistical power based upon a sample size of N=150 evaluable subjects (with post-procedure data) are provided for each respective endpoint.

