#### **9.11 Plans for Interim Analysis**

This study is a group sequential design in which one primary endpoint interim analysis will be conducted after N=160 subjects have been enrolled and followed through 6 months post-procedure. The purpose of the interim analysis will be to determine whether or not to terminate the trial early for futility or tentative success. This analysis will be a test of the primary efficacy endpoint only, and will be conducted after N=160 subjects have been enrolled and have reached 6 months post-procedure. LOCF imputation methodology will be utilized for subjects who do not have 12 month post-procedure data, so that 6 month primary endpoint data will serve as a surrogate for 12 month data for subjects who have not yet reached 12 months post-procedure.

The trial will stop early and will be deemed to be tentatively successful if the two-sided unadjusted p-value for this primary efficacy endpoint analysis is below 0.031. If the stopping rule is met for the trial to stop early for tentative success, a final confirmatory analysis will be conducted when all subjects have reached 12 months post-procedure; a p-value threshold of 0.031 will be used for this final confirmatory analysis. The trial will stop early for futility and it will be decided that the study would not have been successful even if the study would have continued to an enrollment of N=320 if the two-sided unadjusted p-value for this primary efficacy endpoint analysis is above 0.358. If neither of these criteria are met, or if the confirmatory analysis for early success is not satisfied, then enrollment will commence until the total sample of N=320 subjects have been enrolled (including the original N=160), and the final endpoint analysis will be conducted after all 320 subjects have reached 12 months post-procedure. In the case that the study continues to a full enrollment of N=320, the study will be deemed to be a success if the two-sided unadjusted p-value for the final primary efficacy endpoint analysis is below 0.031.

If a decision is made to stop the trial early for either futility or tentative success, follow-up will continue through 12 months post-procedure for all enrolled subjects. Further details of this planned interim analysis are provided in sections 9.1 (Study Design), 9.3 (Levels of Significance), 9.7 (Hypotheses), and 9.9 (Sample Size Justification).

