### **15.2 Premature End**

The study may be discontinued or put on “hold” because of:

- New findings invalidate the earlier positive benefit-risk assessment.
- The time schedule (recruitment phase) cannot be met (e.g. more than doubling of recruitment time).
- The Sponsor decides to discontinue the study at any time.

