5.4 Safety Follow-up after 12 Months Post-Procedure

According to the Close Out Plan, all enrolled and treated subjects will be required to complete follow-up visits through 12 months post-procedure. Hence, only a small number of subjects will have additional safety follow-up data post 12 months. AEs that started after 12-month follow-up will only be listed.

6. Levels of Significance

Protocol specified tests of hypotheses of the primary endpoints at the planned 2.5% significance level will not be conducted due to early termination of the study prior to enrollment of the planned sample size. Two-sided confidence intervals will be computed at a 95% confidence level but are not intended for inference.

7. Analysis Sets

The following analysis sets are defined for the study.

- Modified Intent-to-Treat (mITT) Analysis Set

The mITT Analysis Set consists of all consented (enrolled) subjects who meet all pre-procedure angiographic eligibility criteria, and in whom treatment with the Enterprise device is attempted.

8. Sample Size Justification

This study was originally planned at a total sample size N=320, with an interim analysis for an early stop (either due to futility or tentative success) at N=160 when subjects were enrolled and followed for a minimum of 6-month post-procedure.

However, as the study will be terminated early due to low enrollment, the total sample size for the descriptive analyses in the final CSR will be based on the actual enrollment achieved. .

9. Data and Safety Monitoring Board (DSMB)

An independent DSMB was constituted for monitoring the accumulated interim data as the study progresses to ensure subject safety. All safety review procedures were established and agreed upon in the DSMB Charter prior to enrollment of the first subject.

10. Analyses to be Conducted

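### The interim futility rule is an undirected two-sided p > 0.358, so below a true occlusion rate of about 35% a lower rate is stopped less often; separately, the stated overall power leaves out the futility stop.

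*Protocol*

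**What the plan says.** The claim has one direction. Protocol section 9.7 states: "The primary efficacy endpoint analysis will be to demonstrate that the RCAO is significantly greater than a performance goal (PG) of 35" (per cent), with the alternative RCAO > 35%.

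The interim rule has none. The Overview (Sample Size Determination) tests RCAO against 35% with an unadjusted two-sided normal-approximation p-value. Below 0.031 is tentative success; for the other limb the study "will terminate early for futility if this p-value is greater than 0.358". Section 9.11 repeats that the trial stops for futility "if the two-sided unadjusted p-value for this primary efficacy endpoint analysis is above 0.358". Otherwise enrollment continues to 320.

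The operating-characteristics table (section 9.9, printed under the dataset flow diagram heading) covers true rates from 35% to 50%. Its text says: "The likelihood of stopping early for futility is approximately 54.8% if the RAO in the patient population is 37" (per cent), and "An estimate of overall statistical power is 87.7% if the true RAO is 44% in the patient population". The Overview gives the same 87.7% as the power at the final endpoint if the study goes on to full enrollment.

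**The concern.** A futility rule should remove the results least likely to end in success. A two-sided p-value is large when the observed rate is close to 35% and small when it is far from 35% on either side. An undirected rule therefore stops the middling results and lets clearly poor ones through. In the Protocol's setting that would mean enrolling up to 160 more subjects after a result with very little prospect of success.

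The second concern is the arithmetic of the table. The text applies the futility stop without qualification. The overall power and type I error should then be those of a design in which the stop is applied, and they should agree with the table's other columns.

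**Working it through.** **Inputs.** Null rate 0.35 (section 9.7). Two-sided thresholds 0.031 and 0.358 (Overview, section 9.11). Evaluable subjects: 150 at the interim, 300 at the final analysis (Overview). Outcomes are taken as binomial.

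**Step 1: which counts stop.** z = (x/150 − 0.35) / √(0.35 × 0.65 / 150), with denominator 0.0389.

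| Occlusions of 150 | two-sided p | Rule as written |
|---|---|---|
| 39 | 0.021 | p < 0.031 |
| 40 | 0.032 | continue |
| 45 | 0.199 | continue |
| 47 | 0.346 | continue |
| 48 | 0.441 | stop |
| 52 | 0.932 | stop |
| 57 | 0.441 | stop |
| 58 | 0.346 | continue |
| 66 | 0.021 | tentative success |

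The stop band is 48–57 (32% to 38%), and 40–47 continue. A count of 39 or fewer literally meets the tentative-success limb. It continues only if success is read as upper-tail. The table does read it so: P(X ≥ 66) at a true 35% is 1.4%, its early-success figure.

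**Step 2: reproduce the futility column, then go below 35%.** Undirected: P(48 ≤ X ≤ 57). Directional: P(X ≤ 57).

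| True rate | Stated | Undirected | Directional |
|---|---|---|---|
| 30% | not tabulated | 31.0% | 98.6% |
| 32% | not tabulated | 48.1% | 95.0% |
| 35% | 60.8% | 60.8% | 80.5% |
| 37% | 54.8% | 54.8% | 63.5% |
| 40% | 32.2% | 32.3% | 34.0% |
| 44% | 8.0% | 7.9% | 8.0% |

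All ten stated values agree with the undirected band to within 0.1 point. At 35% and 37% the directional rule is clearly excluded. The column for success if not stopped points the same way. Its 2.9% and 12.4% at 35% and 37% are reproduced only if low counts continue; a directional rule gives 6.0% and 15.8%.

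**Step 3: the ordering of results.** Final success needs 123 of 300 (p = 0.029; 122 gives 0.040). Assume that interim outcomes do not change by 12 months and that the true rate is 44%. From 45/150, 78 of the next 150 are needed, with probability 3.0%. From 52/150, 71 are needed, with probability 22.9%. The rule continues the first and stops the second.

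**Step 4: the overall column.** With the stop applied, overall success = early success + (100 − early success − futility) × success if not stopped. From the table's own entries:

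- 44%: 53.2 + (100 − 53.2 − 8.0) × 0.805 = 53.2 + 31.2 = 84.4%; stated 87.7%.
- 42%: 33.9 + 48.5 × 0.626 = 64.3%; stated 68.1%, the largest gap (3.8 points).
- 35%: 1.4 + 37.8 × 0.029 = 2.5%; stated 2.7%.

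Exact calculation that ignores the stop gives 87.6% and 2.7%, so that is how the column was made. With the stop applied it gives 84.4% and 2.5% under both the undirected and the directional rule.

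**Step 5: the label on 87.7%.** For power given continuation, the table's entry at 44% is 80.5%. A stand-alone test of 300 subjects has 86.6%. Neither is 87.7%, which is the chance of success at the interim or the final analysis with the futility stop ignored.

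**Robustness.** With all 160 evaluable, the band is 51–61, with 63.8% at 35% and 31.9% at 30%. A continuity correction widens the band to 47–58 but gives 69.6% at 35%, which does not match the table.

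**The case against.** The strongest reply is that direction was plainly intended: the alternative is RCAO > 35%, and the early-success column uses the upper tail only. That stands for the success limb. For futility the table refutes it, because 60.8% and 54.8% are the undirected probabilities.

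A second reply is that the rule behaves properly over the range that the Protocol tabulates. That is correct. From 50% down to 35% the chance of a futility stop rises steadily, and at 44% or more the missing direction moves it by 0.1 point or less. A reader might infer that a worse device is always stopped less often; this holds only below about 35%.

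Third, leaving a futility stop out of the type I error is conservative, 2.7% against 2.5%. This also stands. A reader might infer that the missing direction inflates type I error or lowers power; it does neither. Only the stated power is optimistic, and the cause is the omitted stop.

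A reader might also infer that 39 or fewer occlusions would be declared a success. The wording permits that, but the alternative hypothesis and the table do not support it.

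Finally, section 15.2 limits the practical effect by listing among the grounds for a premature end: "The Sponsor decides to discontinue the study at any time". And SAP section 6 says that the hypothesis tests "will not be conducted due to early termination of the study prior to enrollment of the planned sample size"; section 10.5 cancels the interim analysis. These facts limit the consequence but do not correct the rule or the figures.

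**Conclusion.** The point holds, as a minor one. The futility rule lacks a direction, and the Protocol's own table was computed that way. At a true 35%, 19.7% of trials would have 47 or fewer occlusions and escape the stop. If all of these continue automatically, the expected excess is 160 × 0.197 ≈ 31 subjects; at 37%, 40% and 44% it is about 14, 3 and 0.2.

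Separately, overall power at 44% is 3.3 points too high for a design in which the stop is applied, and the Overview mislabels 87.7%.

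The stop-band figures depend only on the interim count, taken as binomial with 150 evaluable subjects. The overall and final-success figures also count tentative success as success, as the table does, and carry interim outcomes unchanged into the final count. Section 9.11 says that "6 month primary endpoint data will serve as a surrogate for 12 month data", and the documents give no rate of change between the two visits. No descriptive analysis that remains in the SAP is affected.

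**What to change.** 1. In the Overview and sections 9.7 and 9.11, state the limbs on the signed statistic. Tentative or final success: observed rate above 35% and two-sided p < 0.031. Futility (Overview and 9.11): z < 0.919, that is one-sided p > 0.179, or 57 or fewer of 150.
2. In the table, replace the futility and success-if-not-stopped columns with those below, and change the 54.8% at 37% in the text to 63.5%.
3. Either declare the futility stop non-binding and keep 87.7% and 2.7% as overall figures, or apply it and restate the overall column as in the last column below.
4. In either case, relabel the Overview's 87.7% as overall power (interim or final). If the stop is applied, the figure there becomes 84.4%.

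| True rate | Futility, directional | Success if not stopped, directional | Overall, stop applied |
|---|---|---|---|
| 35% | 80.5 | 6.0 | 2.5 |
| 37% | 63.5 | 15.8 | 9.6 |
| 40% | 34.0 | 42.3 | 38.4 |
| 42% | 18.2 | 63.2 | 64.3 |
| 43% | 12.4 | 72.6 | 75.5 |
| 44% | 8.0 | 80.6 | 84.4 |
| 45% | 5.0 | 87.0 | 90.9 |
| 46% | 2.9 | 91.7 | 95.0 |
| 47% | 1.6 | 95.0 | 97.4 |
| 50% | 0.2 | 99.2 | 99.8 |

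The last column comes from the stated table by the Step 4 formula; exact calculation under either rule agrees to within 0.15 point.

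The cost is a few phrases in three places, two or three table columns and one sentence on whether the stop is binding. Sample size, success thresholds and the SAP's descriptive analyses do not change.

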10.5 Plans for Interim Analysis

According to the Study Close Out Plan, the planned interim analyses will not be conducted.

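### The 87.7% power carries two incompatible labels and leaves out the futility stop; under the written rule it is 84.4% overall and 80.5% if the study continues.

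*Protocol*

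**What the plan says.** The design tests the rate of complete aneurysm occlusion against a performance goal of 35%, with a first look at about 150 evaluable subjects and a final look at about 300. At either look, success requires that "the unadjusted 2-sided normal approximation p-value for testing the primary effectiveness endpoint (RCAO vs. the PG of 35%) is less than 0.031". At the interim the study "will terminate early for futility if this p-value is greater than 0.358". Protocol Section 9.11 repeats this without leaving a choice: "The trial will stop early for futility and it will be decided that the study would not have been successful" even at full enrollment.

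The overview (Sample Size Determination) states: "The statistical power at the final endpoint (if the study continues to full enrollment) is 87.7" percent, for a true rate of 44% and 300 evaluable subjects.

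The operating-characteristics table, printed after the dataset flow diagram in Section 9.9, has separate columns for overall power, early success, success at full enrollment when neither stop occurred, and futility stopping. Its 44% row reads 87.7%, 53.2%, 80.5% and 8.0%. The text below it says: "An estimate of overall statistical power is 87.7% if the true RAO is 44% in the patient population". That text also treats futility stopping as a real outcome ("The likelihood of stopping early for futility is approximately 54.8% if the RAO in the patient population is 37" percent) and says of the error rate that "this estimated Type 1 error rate is 2.7% (2-sided), which is below 5" percent.

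SAP Section 10.5 later records that "the planned interim analyses will not be conducted".

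**The concern.** One number has two definitions. In the overview it is conditional on continuing to full enrollment; in the statistics section it is unconditional, with success possible at either look. For the conditional quantity the table prints 80.5%.

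The overall column also does not fit its neighbours. Overall success has only two routes: early success, or continuing past both stopping rules and then succeeding. The three other columns fix that total, and it is not the printed one. The 47% row shows the conflict most plainly. Overall success (98.6%) and a futility stop (1.6%) exclude each other under the written rule, yet they add to 100.2%.

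The 87.7% is the power quoted in support of the N=320 design. If it omits a stop that the protocol requires, the design was presented as more likely to detect a 44% rate than it is.

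**Working it through.** **Inputs.** Performance goal 35%; success if two-sided p < 0.031; futility if two-sided p > 0.358; 150 evaluable at the interim and 300 at the final look; true rate 44%. All are from the overview (Sample Size Determination).

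**Boundaries.** The test is z = (x/n − 0.35) / √(0.35 × 0.65 / n), two-sided, without continuity correction.
- Interim success: x ≥ 66 of 150.
- Interim futility: x from 48 to 57 of 150.
- Final success: x ≥ 123 of 300.

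**Reproducing the printed 44% row** by exact enumeration of both stages:

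| Quantity | Printed | Exact |
|---|---|---|
| Early success | 53.2% | 53.15% |
| Futility stop | 8.0% | 7.94% |
| Success given neither stop | 80.5% | 80.42% |
| Overall, futility stop ignored | 87.7% | 87.63% |
| Overall, futility stop applied | not printed | 84.44% |

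Three columns reproduce with the rules as written. The overall column reproduces only if studies inside the futility region carry on to 300 and may still succeed.

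**The same result from the printed columns:** overall = early success + (1 − early success − futility) × success given neither stop = 53.2% + (100% − 53.2% − 8.0%) × 0.805 = 53.2% + 38.8% × 0.805 = 84.4%.

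**Where the difference lies.** 87.63% − 84.44% = 3.19 points. It comes from the 7.94% of studies in the futility region, of which 3.19 / 7.94 = 40% would have succeeded if continued. The 87.6% cannot be obtained by deleting the 8.0% from the formula above. That would apply the 80.5% success rate to studies that were doing poorly at the interim, and gives 90.9%.

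**All rows (overall power, %):**

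| True rate | Printed | Exact, futility ignored | Exact, futility applied |
|---|---|---|---|
| 35% | 2.7 | 2.70 | 2.49 |
| 37% | 10.6 | 10.57 | 9.67 |
| 40% | 41.4 | 41.32 | 38.25 |
| 42% | 68.1 | 68.05 | 64.17 |
| 43% | 79.1 | 79.19 | 75.49 |
| 44% | 87.7 | 87.63 | 84.44 |
| 45% | 93.3 | 93.32 | 90.83 |
| 46% | 96.8 | 96.74 | 94.97 |
| 47% | 98.6 | 98.56 | 97.42 |
| 50% | 99.9 | 99.94 | 99.75 |

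The printed column follows the futility-ignored values to within 0.1 point in every row.

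**The 47% row.** 98.6% + 1.6% = 100.2%. The lowest sum that rounding allows is 98.55% + 1.55% = 100.1%. Solving the printed row for success given neither stop gives (98.6 − 79.3) / (100 − 79.3 − 1.6) = 101.0%.

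**Single-look reading of the overview sentence.** One test at 300 subjects with p < 0.031 has power 86.6% exactly (85.7% by normal approximation), so this does not give 87.7% either.

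**Type I figure.** At a true rate of 35%, the chance of a false success claim is 2.70% without the futility stop and 2.49% with it. Both are upper-tail probabilities. The two-sided error with the futility stop applied is 4.71%, so the statement that two-sided alpha is below 0.05 holds under the mandatory rule.

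**The case against.** The best defence is that the overall column treats futility as non-binding, a common convention, and that every column is correct on its own basis. The text that introduced the table does not survive in the available copy, and Section 9.11 refers to a sample size justification in 9.9 that is not there, so such a statement may have existed. On that basis the 47% row mixes conventions and contains no miscalculation, because the two events may overlap. This much stands: the column was computed consistently, with the futility stop left out. It does not rescue the plan. The surviving text says twice that the trial will stop, and no convention makes the overview label right.

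The overview sentence could also mean a single test at full enrollment. With 320 subjects that gives 87.7%. But the sentence specifies 300 evaluable, and the statistics section calls the same number overall power.

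Two further points are fair. The 84.4% is not the power of the complete written procedure, because it counts interim success as final. And the study ended early for low enrollment, so no decision now depends on the figure. Both limit the weight of the point, but the stated power remains wrong.

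**Conclusion.** The concern holds. At a true rate of 44%, overall power under the written rules is 84.4%, which is 3.3 points below the stated 87.7%; type II error is 15.6% rather than 12.3%. Power given continuation to full enrollment is 80.5%, which is 7.2 points below what the overview says. At 42% the overall figure is 64.2% against 68.1%, and at 40% it is 38.3% against 41.4%.

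These figures assume 150 and 300 evaluable subjects, a binding futility stop, and, as the table does, that the interim outcome equals the 12-month outcome. They leave out the 12-month confirmatory test and the resumed enrollment if it fails. As an assumption not found in the documents, suppose 2% to 10% of subjects change occlusion status in each direction between 6 and 12 months. Simulated overall power with those steps included is then 83.7% down to 82.1%.

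Alpha control is not in question, and the 2.7% needs only a correct label. Because the SAP has dropped the interim analysis and the tests, the correction concerns the design properties on record.

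**What to change.** - **Overview, Sample Size Determination:** state overall power of about 84.4% at a true rate of 44%, and about 80.5% if the study continues to full enrollment.
- **Text below the table:** change the overall power at 44% from 87.7% to about 84.4%.
- **Table, overall column, from 35% to 50%:** replace with 2.5, 9.7, 38.3, 64.2, 75.5, 84.4, 90.8, 95.0, 97.4, 99.7. These are the exact values; rebuilding from the rounded printed columns moves some rows by 0.1.
- **Note to the table:** say that the figures apply the futility stop, count tentative interim success as final, and do not model the confirmatory test or resumed enrollment.
- **Type I label:** describe the figure as one-sided, 2.5% with the futility stop and 2.7% without.

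The cost is two sentences, one column with its note, and one label. The 0.031 threshold, the sample size and the SAP analyses do not change.
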